18.3. SECONDARY EFFICACY

The secondary efficacy analyses, as defined in Table J, will be performed for the ITT. For all secondary endpoints, a similar estimand to the one used for the primary analysis will be employed. That is, the estimand of interest will be based on overall mean monthly estimates across/within the double-blind period and will be based on all available data during that period (even if collected after study intervention discontinuation). Additionally, baseline values must also be available.

Table J: Secondary Efficacy Variables and Analysis Methods

Efficacy Endpoint/Variable	Analysis
Overall mean change from baseline in the number of monthly migraine headache days across the 3-month double-blind treatment period	MMRM
The percentage of participants with X% reduction from baseline in monthly migraine headache days across the 3- month double-blind treatment period. (X=75 or 100)	GLIMMIX
The mean change from baseline in the number of monthly migraine headache days at Months 3, 2, and 1	MMRM
The overall mean change from baseline in the number of monthly migraine headache days requiring medication for the acute treatment of migraine or headache across the 3-month double-blind treatment period	MMRM
The mean change from baseline in the Role Function-Restrictive (RF-R) domain score of the Migraine-Specific Quality of Life Questionnaire version 2.1 (MSQ v2.1) at Month 3	ANCOVA
Changes from baseline to Month 3 in MSQ v2.1 total score, and Role Function-Preventive (RF-P) and Emotional Function (EF) domain scores	ANCOVA
Changes from baseline to Month 3 in MIDAS (Migraine Disability Assessment) total score	ANCOVA

Document: **CCI**

Author: **PPD**

Version Number:

3.0

Version Date:

19May2023

CCI

Abbreviations: G.LIMMIX = Generalized linear mixed model (for binary variables); MMRM = Mixed models repeated measures; ANCOVA= Analysis of Covariance

18.3.1. MISSING DATA METHODS FOR SECONDARY EFFICACY VARIABLE(S)

For the repeated measures analyses, the model parameters are simultaneously estimated using restricted likelihood estimation incorporating all of the observed data. Estimates have been shown to be unbiased when the missing data are missing at random.

Please refer to Section 18.1.1 for approach of handling missing diary data for derivation of the number of migraine headache days and other efficacy measures (with the exception of migraine attacks) derived from ePRO data per 30-day period.

18.3.2. ANALYSIS OF SECONDARY EFFICACY VARIABLES

18.3.2.1. Analysis of Key Binary Secondary Efficacy Endpoints

Dichotomous outcomes will be analyzed using a the same GLIMMIX as pseudo- likelihood-based mixed effects repeated measures analysis used for the primary endpoint. The GLIMMIX procedure will include the fixed, categorical effects of treatment, month, and treatment-by-month interaction, as well as the continuous, fixed covariate of baseline for the variable of interest. Please refer to Section 18.2.3 for details.

For the repeated binary efficacy measure where the objective is to assess the proportion of patients with X% response during the 3-month double-blind treatment phase, the endpoint for comparing galcanezumab with rimegepant will be estimated as the treatment main effect from the categorical MMRM analysis assessing the average response rate across Months 1, Month 2 and Month 3.

18.3.2.2. Continuous Efficacy Measures

Continuous efficacy variables with repeated measures will be analyzed using a restricted maximum likelihood (REML)-based mixed models repeated measures (MMRM) technique and will include the fixed, categorical effects of treatment, month, and treatment-by-month interaction, well as the continuous fixed covariates of baseline number of migraine headache days and baseline-by-month interaction. This model is referred to as the MMRM model throughout this document.

Document: **CCI**

Author: **PPD**

Version Number:

3.0

Version Date:

19May2023

CCI

The Kenward-Roger (Kenward and Roger 1997) approximation will be used to estimate denominator degrees of freedom. Wherever possible an unstructured covariance matrix will be used to model the correlation structure among repeated measures. If the model does not converge with both the Hessian and the G matrix being positive definite under the default fitting algorithm used by PROC MIXED, the Fisher scoring algorithm will be implemented by specifying the SCORING option in SAS. If the model still fails to converge, the model will be fit using covariance matrices of the following order specified by a decreasing number of covariance parameters until convergence is met:

- Heterogeneous Toeplitz
- Heterogeneous First-order autoregressive
- Toeplitz
- First-order autoregressive

When the unstructured covariance matrix is not utilized, the sandwich estimator (Diggle and Kenward 1994) will be used to estimate the standard errors of the fixed effects parameters. The sandwich estimator is implemented by specifying the EMPIRICAL option in SAS®. When the sandwich estimator is utilized, the Kenward-Roger approximation for denominator degrees of freedom cannot be used. Instead, the denominator degrees of freedom will be partitioned into between-subject and within-subject portions by the DDFM=BETWITHIN option in SAS®. SAS® PROC MIXED will be used to perform the analysis.

For continuous efficacy variables without repeated measures, an analysis of covariance (ANCOVA) which contains the main effects of treatment, and the continuous fixed covariate of baseline. Type III sum-of-squares for the LSMeans will be used for the statistical comparisons.

For continuous secondary efficacy measures where the objective is to assess overall mean change during the 3-month double-blind treatment period, the endpoint for galcanezumab compared with rimegepant will be estimated as the treatment main effect from the MMRM analysis assessing the average treatment effect across Months 1, 2, and 3.

The statistical comparisons for the primary efficacy endpoint and the key secondary endpoints will be carried out in the hierarchical order. This means that statistically significant results for the comparison in the higher rank (primary, then ranked secondary variables) are

Document: **CCI**

Author: **PPD**

Version Number:

3.0

Version Date:

19May2023

CCI

required to initiate the testing of the next comparison in the lower rank. Since a step-down procedure is used, each comparison will be tested at a significance level of 0.05 and an overall alpha level of 0.05 will be preserved.

The order of objectives/comparisons may change (with the exception of the primary objective). Should such a change take place, the final hierarchical order used/multiplicity adjustment approach employed to ensure overall 0.05 alpha-level control will be documented within an approved final SAP prior to study unblinding.

If galcanezumab is statistically superior to rimegepant on the primary objective, the following key secondary endpoints will be tested with adjustment for multiplicity:

- The overall mean change from baseline in the number of monthly migraine headache days across the 3-month double-blind treatment period. (Using MMRM method)

From above model, the mean change from baseline in the number of monthly migraine headache days can be obtained at:

- Month 3
- Month 2
- Month 1
- The percentage of participants with $\geq 75\%$ reduction from baseline in monthly migraine headache days across the 3-month double-blind treatment period. (Using GLIMMIX procedure)
- The overall mean change from baseline in the number of monthly migraine headache days requiring medication for the acute treatment of migraine or headache across the 3-month double-blind treatment period. (Using MMRM method). For this analysis, medication use will be based on the response to question 12 in the diary.

Other key secondary endpoints will be analyzed using corresponding analysis methods as specified:

- The mean change from baseline in the Role Function-Restrictive (RF-R) domain score of the Migraine-Specific Quality of Life Questionnaire version 2.1 (MSQ v2.1) at Month 3. (Using ANCOVA method)
- The percentage of participants with 100% reduction from baseline in monthly migraine

Document: **CCI**

Author: **PPD**

Version Number:

3.0

Version Date:

19May2023

CCI

headache days across the 3-month double-blind treatment period. (Using GLIMMIX procedure)

18.3.2.3. Analysis of Changes from Baseline to Month 3 on Disability and Health-related Quality of Life

There are two changes from baseline to Month 3 on disability and health-related quality of life to be analyzed:

- MSQ v2.1 total score, and Role Function-Preventive (RF-P) and Emotional Function (EF) domain scores
- MIDAS (Migraine Disability Assessment) total score

For the above continuous efficacy variable without repeated measures, an ANCOVA model which contains the main effects of treatment, and the continuous fixed covariate of baseline. Type III sum-of-squares for the LS Means will be used for the statistical comparisons.

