7.1. ADJUSTMENTS FOR COVARIATES IN ANALYSES

For both binary (e.g. response rates) and continuous analyses (e.g. changes in headache days), continuous baseline measure will be specified in the model which will include the fixed, categorical effects of treatment, month, and treatment-by-month interaction, as well as the continuous, fixed covariate of baseline monthly migraine headache days value

If the variable to be analysed relies on migraine headache day data, then use the continuous value of baseline migraine headache days as covariate, or if the variable being analyzed does not rely on migraine headache day data, then the model will use the baseline number of migraine headache days category (<8 vs ≥ 8) as a covariate for the MMRM, AN(C)OVA, and GLIMMIX procedure .

Document: CCI

Author: PPD

Version Number:

3.0

Version Date:

19May2023

CCI

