11. DISEASE HISTORY

The following disease history characteristics will be summarized overall and by treatment group based on the ITT:

- Duration of migraine illness (years) – calculated relative to date of first dose of study treatment.
- Migraine and/or headache measures per 30-day baseline period.
 - number of migraine headache days
 - number of migraine headache days with acute (abortive) medication use
 - number of migraine headache hours
 - number of migraine attacks
 - number of headache days
 - number of moderate-severe headache days
 - number of headache hours
 - mean severity of migraine headaches
 - number of migraine headache days with aura
 - number of migraine headache days with nausea and/or vomiting
 - number of migraine headache days with photophobia and phonophobia
 - number of migraine headache days with prodromal symptoms other than aura
 - Prior migraine preventive treatment:
 - Without prior migraine preventive treatment
 - With prior migraine preventive treatment and did not fail
 - With prior migraine preventive treatment and failed at least 1 medication
 - With prior migraine preventive treatment and failed at least 2 medications.
 - Number of prior migraine treatment failed: 1, 2, 3, ...
- Baseline number of migraine headache day category (<8 versus ≥8, based on patient diary)
- PGI-S
- Alcohol, tobacco, caffeine, and nicotine use

 Document: **CCI**

 Author: **PPD**

Version Number:

3.0

Version Date:

19May2023

CCI

Comparisons between treatment groups will be performed using Fisher's exact test for categorical data and ANOVA with treatment as independent variables in the model for continuous data.

All disease history characteristics will be listed.

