Number of migraine headache days with acute (abortive) medication use is calculated as the number of calendar days in a 30-day period on which migraine or probable migraine occurs and acute (abortive) medication is used (based on the response to question 12 in the daily diary questions, Table G).

Weekly migraine headache days is defined as is calculated as the number of migraine headache days in a 7-day period on which a migraine headache occurs. For each month, the first 7 calendar days will be counted as week 1, the second 7 calendar days will be counted as week 2, the third 7 calendar days will be counted as week 3, and the rest of days will be counted as week 4.

Number of migraine headache hours is calculated as the total number of headache hours in a 30-day period on days when a migraine or probable migraine occurs.

Number days with acute (abortive) medication use is calculated as the number of calendar days in a 30-day period on which an acute (abortive) medication is used (based on the response question 12 in the in the daily diary questions, Table G).

Number of headache days is calculated as the number of calendar days in a 30-day period on which a headache occurs (includes migraine, probable migraine, and non-migraine).

Number of moderate to severe headache days is calculated as the number of calendar days in a 30-day period on which a headache occurs with a moderate or severe severity (based on Q3 response, Table G.)

Number of migraine attacks per 30-day period is calculated as the number of sets of consecutive days with migraine or probable migraine separated by at least one migraine-free day. For example, a migraine or probable migraine starting on 5JAN and ending on 6JAN will result in a migraine/probable migraine-free day on 7JAN (assuming that there is no migraine/probable migraine on 7JAN). This will count as 1 migraine attack that started on 5JAN and ended on

Document: **CCI**

Author: **PPD**

Version Number:

3.0

Version Date:

19May2023

CCI

6JAN. For a migraine attack that begins in one 30-day period but ends in another, only 1 migraine attack will be counted in the first of the 2 periods. For example, in the case of 7 days of consecutive migraine/probable migraine headache with 3 days in the baseline period and 4 days in Month 1, only 1 migraine attack will be counted in the baseline period; the 4 days of migraine/probable headache in Month 1 will not be counted as a migraine attack in Month 1.

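### The model for migraine days with acute medication (H07) omits that variable's own baseline, and SAP 7.1 and 18.3.2.2 disagree on the covariates for MSQ RF-R (H08)

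*SAP*

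**What the plan says.** **H07.** Table J and the list of key secondary endpoints in SAP 18.3.2.2 assign the change in migraine headache days with acute medication to the MMRM. SAP 18.3.2.2 builds that MMRM on "continuous fixed covariates of baseline number of migraine headache days" plus a baseline-by-month term, and adds: "This model is referred to as the MMRM model throughout this document". SAP 7.1 agrees: "If the variable to be analysed relies on migraine headache day data, then use the continuous value of baseline migraine headache days as covariate". H07 is such a variable. The measures listed after SAP 18.1.2 define it as days "on which migraine or probable migraine occurs and acute (abortive) medication is used".

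H07's own baseline appears in neither rule, although SAP 11 already tabulates the baseline "number of migraine headache days with acute (abortive) medication use".

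**H08.** For a variable that does not rely on migraine days, such as MSQ RF-R, SAP 7.1 says "then the model will use the baseline number of migraine headache days category" (<8 versus ≥8), and it names AN(C)OVA among the models covered. The ANCOVA in SAP 18.3.2.2 is one "which contains the main effects of treatment, and the continuous fixed covariate of baseline", with no category term.

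**Other wording.** SAP 18.3.2.1 uses the baseline of the variable of interest for the binary secondaries. The exploratory MMRMs in SAP 18.4.3 and the MMRM in protocol 9.3.1 say only baseline. SAP 3.3 lists added exploratory endpoints as the only changes from the protocol.

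**The concern.** H07 is a change score. When its own baseline is left out of the model, whatever part of that baseline total migraine days do not explain stays in the residual. Treated migraine days are a subset of migraine days, so adjusting for the total removes the shared part of a chance imbalance. It leaves the part specific to how often a participant treats an attack.

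H07 is step 7 of the fixed sequence in SAP 7.4. If H01 to H06 are all rejected, a missed H07 ends testing, and neither H08 (MSQ RF-R) nor H09 (100% response) can be claimed.

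For H08 the issue is different. Read together, the two sections allow three models: RF-R baseline alone, the category alone, or both. Each can give a different p-value in an alpha-controlled test. The primary endpoint and H02 to H06 are unaffected, because baseline migraine days are the right covariate there.

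**Working it through.** **What the plan gives.** The only power figure (more than 85%, 12-point difference, about 575 participants; protocol 9.5) is for the primary response endpoint. There is none to reproduce for H07 or H08, and no SD or correlation for either. The inputs below are assumptions, shown as ranges.

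**H07, closed form.** Let Y be follow-up, X2 own baseline and X1 baseline total migraine days, with
- r = corr(Y, X2), taken as 0.3 to 0.6
- q = corr(X1, X2), taken as 0.6 to 0.9
- s = corr(Y, X1)
- k = SD(Y)/SD(X2)

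Residual variance in units of Var(X2):
- SAP model (change adjusted for X1): V1 = k² + 1 − 2kr − (ks − q)²
- Own baseline added: V2 = k²[1 − (r² + s² − 2rsq)/(1 − q²)]

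With k = 1 and s = rq (total days predict follow-up only through own baseline), V2 reduces to 1 − r²:

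| r | q | V1 | V2 | V1/V2 | Assumed 80% power becomes |
|---|---|---|---|---|---|
| 0.6 | 0.9 | 0.8 − 0.36² = 0.670 | 0.640 | 1.05 | 78% |
| 0.5 | 0.7 | 1.0 − 0.35² = 0.878 | 0.750 | 1.17 | 74% |
| 0.3 | 0.6 | 1.4 − 0.42² = 1.224 | 0.910 | 1.34 | 68% |

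Power is Φ(2.802/√(V1/V2) − 1.960), where 2.802 = 1.960 + 0.842.

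Other assumptions:
- k = 1 and s = r (total days predict follow-up as well as own baseline does): 1.14 to 1.48, power 75% to 64%.
- k from 0.8 to 1.2 and s from rq to r: 1.02 to 1.89, power 79% to 53%. The top value needs r = s = q = 0.6 and k = 0.8 together.

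The share of own-baseline variance not explained by total days is 1 − q²: 19% at q = 0.9 and 64% at q = 0.6.

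**H07, simulation.** 2,000 trials per setting, n = 518 (575 × 0.9 = 517.5), 1:1, complete data. In that case the overall MMRM effect equals ANCOVA on the 3-month mean. The power columns use assumed effects of about 0.74, 0.66, 0.54 and 0.46 day, from top to bottom.

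| Migraine days treated | corr(X1, X2) | Variance, own ÷ total | Power, total days | Power, own baseline |
|---|---|---|---|---|
| 95% | 0.96 | 0.96–0.97 | 80% | 82% |
| 85% | 0.84 | 0.88–0.90 | 73% | 80% |
| 70% | 0.67 | 0.76–0.80 | 63% | 73% |
| 60% | 0.54 | 0.69–0.74 | 52% | 69% |

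Null rejection with total days alone was 4.5% to 5.6%, consistent with 5%. Mean estimates under an effect agreed across the adjusted models to within 0.01 day. Using both covariates instead of own baseline alone changed the variance by a factor of 0.998 to 1.002, so keeping both costs nothing measurable.

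**H08.** If the category were used instead of the RF-R baseline, and is taken as uncorrelated with RF-R, the ratio at k = 1 is (2 − 2r)/(1 − r²) = 2/(1 + r). That is 1.25 at r = 0.6 and 1.54 at r = 0.3, so 80% power becomes 71% to 62%. If the category is added to the RF-R baseline, there is no such loss.

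**The case against.** **Validity is conceded.** The H07 rule is fixed in advance, so what remains could be called a preference between covariates. That is right about bias and alpha. But the omitted covariate is the baseline of the analysed variable, it is already collected, and adding it costs nothing measurable.

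**The wording may be looser than it looks.** SAP 7.1 opens by saying that a "continuous baseline measure will be specified in the model", protocol 9.3.1 says only baseline, and SAP 3.3 declares no covariate change. Perhaps 18.3.2.2 was written with H02 in mind. However, the same opening sentence of 7.1 goes on to name baseline migraine headache days, and the explicit, document-wide definition in 18.3.2.2 outranks generic phrases elsewhere. The wording in 18.3.2.1 is weak evidence of inconsistency, since the variable behind the 75% and 100% responses is migraine days.

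**Unconditional power overstates the harm.** H07 is tested only after H02 and the three monthly tests succeed on a closely related variable. An illustrative simulation of passing H02, H04 to H06 and then H07 (assumed inputs, n = 518) put the loss at 0.4 to 0.7 percentage points at a baseline correlation of 0.91, 2 to 3 at 0.80, 4 to 9 at 0.63 and 7 to 18 at 0.52. This stands: the practical loss is smaller than the power column suggests when the two baselines are nearly collinear. It is still real when they are not.

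**The H08 replacement case is unlikely.** SAP 7.1 does not say that the category replaces the baseline, and 18.3.2.2 requires a continuous baseline. Own baseline plus stratum is the natural combined reading, with no loss. This also stands. The H08 half alone would be a request for clarification.

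**Conclusion.** The concern holds. As written, the plan tests H07 without adjusting for its own baseline. This is a matter of efficiency and clarity, with no bias and no inflation of type I error. One caveat applies: with missing months, the missing-at-random assumption is conditional on the modelled variables, and own baseline is not among them.

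The main illustrative range is a residual variance 1.05 to 1.35 times larger than necessary. The loss is trivial if nearly all migraine days are treated with acute medication and material if many are not. The documents do not give that share, so the size cannot be narrowed.

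For H08, the mismatch over the <8/≥8 term is real and leaves a confirmatory model not uniquely specified. It costs precision only if the category displaces the RF-R baseline. The change is worth making before unblinding because it is nearly free and H07 gates the last two claims.

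**What to change.** Before unblinding, put one covariate list per endpoint in SAP 7.1 and repeat it in 18.3.2.2:

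- **Every change-from-baseline MMRM or ANCOVA:** include the analysed variable's own baseline, with its month interaction in the MMRM.
- **H07:** baseline migraine headache days with acute medication and its month interaction, keeping baseline total migraine headache days as an extra covariate.
- **MSQ (RF-R, RF-P, EF, total), MIDAS and PGI-S:** own baseline plus the <8/≥8 stratum, stated explicitly as an addition.
- **H02 to H06:** no change.

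Record any departure from the protocol 9.3.1 models in SAP 3.3.

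The cost is wording only. No new data are needed, since the H07 baseline is already derived for SAP 11. The models give up 3 degrees of freedom in the H07 MMRM (own baseline and its interaction with three months) and 1 in the MSQ ANCOVA, which is negligible at this sample size.

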18.4. EXPLORATORY EFFICACY

The exploratory efficacy analyses will be performed for the ITT. Table K summarizes all the planned secondary efficacy analyses.

Document: CCI

Author: PPD

Version Number: 3.0

Version Date: 19May2023

CCI

Table K: Exploratory Efficacy Variables and Analysis Methods

Efficacy Variables	Analysis
Change from baseline in the Patient Global Impression of Severity (PGI-S) at Month 3	ANCOVA
Change from baseline in the number of monthly moderate to severe headache days across the 3-month double-blind treatment period	MMRM
Change from baseline in the Monthly Total Pain Burden across the 3-month double-blind treatment period	MMRM
50% response rate: 
 Percentage of participants with $\geq 50\%$ reduction from baseline in monthly migraine headache days at Month 3, Month 2, and Month 1 Percentage of participants with $\geq 50\%$ reduction in Weekly migraine headache days at weeks 4, 3, 2, 1 in the months that galcanezumab was superior to rimegepant The initial month at which galcanezumab was superior to rimegepant in the proportion of patients meeting at least a 50% reduction in monthly migraine headache days that is sustained at all subsequent months through Month 3 Percentage of participants with $\geq 50\%$ reduction from baseline in moderate to severe monthly migraine headache days across the 3-month double-blind treatment period 	GLIMMIX
Change from baseline in the number of weekly migraine headache days in the months that galcanezumab was superior to rimegepant	MMRM
Change from baseline in the number of monthly days with acute headache medication use during the 3-month double-blind treatment phase	MMRM
Change from baseline in the number of monthly moderate to severe migraine headache days across the 3-month double-blind treatment period	MMRM

Abbreviations: ANCOVA = analysis of covariance; GLIMMIX = Generalized linear mixed model (for binary variables); MMRM = Mixed models repeated measures.

